4.3. END OF STUDY DEFINITION

A patient is considered to have completed the study if he or she has completed the Treatment Phase and all Follow-up visits (Days 28, 45, and 60).

Discontinuation from CX-4945 does not mean the withdrawal from the study assessments. Patients who discontinued therapy should remain in the study and continue follow-up for key outcomes. The only reasons for study withdrawal are withdrawal of consent and loss to follow-up.

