6.1.5. CX-4945 Dose Modifications

The most common drug related adverse events reported for CX-4945 are predominantly gastrointestinal disorders, including nausea, vomiting and diarrhea. The dose interruption, reduction, and permanent discontinuation for any toxicity are described below. Dose modification instructions provided below do not substitute for an investigator's medical judgement. Investigators should always manage their patients according to their medical judgement based on the particular clinical circumstances.

**Table 3: CX-4945 Dose Modification and Management for Potential Toxicities
(Attributable to CX-4945)**

Grade* (attributable to CX-4945)	Treatment Modifications
Grade 1	Treat on time, dose reduction is not required
Grade 2	Hold until \leq Grade 1, resume at same dose
Grade 3	Hold until $<$ Grade 2, resume at dose reduced by 1 level (200 mg)
Grade 4	Hold until $<$ Grade 2, resume at dose reduced by 1 level (200 mg). Permanent discontinuation can be considered at the Investigator's discretion

* *Toxicity Grading Scale for Healthy Adult and Adolescent Volunteers Enrolled in Preventive Vaccine Clinical Trials: <https://www.fda.gov/media/73679/download>*

- **Dose Reduction:** If a dose-response relationship for toxicity is observed, then a reduced dose can be given to the patient. Dose adjustments will be allowed based on the toxicity, efficacy evaluation, and clinical judgment by a physician.
- **Dose Interruption:** Refer to **Table 3** above. Recovery to acceptable levels must occur to allow CX-4945 continuation.
- **Dose Discontinuation:** Treatment with CX-4945 can be discontinued prematurely due to the following reasons:
 - Disease progression
 - Respiratory failure requiring invasive mechanical ventilation,
 - Shock (defined by SBP < 90 mm Hg, or Diastolic BP < 60 mm Hg), or
 - Multiple organ dysfunction/failure
 - Intolerable toxicity most probably attributable to CX-4945.
 - Withdrawal from the study treatment or participation
 - Pregnancy
 - Significant study therapy non-compliance
 - If any clinical adverse event, laboratory abnormality, or other medical condition or situation occurs that continued treatment under the protocol would not be in the best interest of the patient.

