### 1.1 Visit Adjustment

Visit 6 is End of Treatment (EOT) Visit, Treatment Discontinuation Visit or Early Withdrawal Visit at/before EOT. Data of visit 6 not in its visit window will be shifted to corresponding scheduled visit for analysis as in table below (marked ‘\*’). Visit name will be presented as ‘Adjusted Visit’ for the visits reallocated to its original scheduled visit or the next visit after preceding scheduled visit.

	Visit 6 to Visit 3~6
COVID-19-Related Symptoms	*
Clinical Status - NIAID 8-Point Clinical Progression Outcomes Scale	*
Laboratory Examination	*
Vital Signs, Pulse Oxygen Saturation (SpO2) and COVID-19-Related Clinical Signs	*

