## (4) For Visit Name (in Tables and Figures) and Visit Code (in Subject Data Listing):

Visit No.	Visit Description	Visit Day	Visit Name	Visit Code
1	Screening Visit	-7 ~ -1	Visit 1 (Screening)	V01
2	Treatment Visit (Day 1)	1	Visit 2 (Day 1)	V02D01T
3	Treatment Visit (Day 4)	4 ± 1	Visit 3 (Day 4)	V03D04T
4	Treatment Visit (Day 8)	8 ± 1	Visit 4 (Day 8)	V04D08T
5	Treatment Visit (Day 11)	11 ± 1	Visit 5 (Day 11)	V05D11T
6	End of Treatment (EOT)Visit (Day 14)	14 ± 1	Visit 6 (Day 14, EOT)	V06D14E
7	Follow-up 1 Visit (Day 28)	28 ± 3	Visit 7 (Day 28, F1)	V07D28F
8	Follow-up 2 Visit (Day 45)	45 ± 3	Visit 8 (Day 45, F2)	V08D45F
9	Follow-up 3 Visit (Day 60)	60 ± 3	Visit 9 (Day 60, F3)	V09D60F
	Unscheduled Visit	-	-	UV

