### 14.1.8 Best Supportive / Standard Of Care Procedures

Population: Intent-to-Treat Population

Characteristics	Treatment Group	P-value
- Repeat Duration: Prior Procedure, Concomitant Procedure, Post Procedure		
. Repeat Variable: Subject with Best Supportive / Standard Of Care Procedures (Multi-Selection by Highest ATC Level Class and ATC Preferred Term)		
N	XXX	C/F
At least one below [Day#:Subj#]	XXX : XXX (XXX.X%)	0.XXXX
Extracorporeal Membrane oxygenation	XXX : XXX (XXX.X%)	0.XXXX
Fluid management	XXX : XXX (XXX.X%)	0.XXXX
Mechanical Ventilation	XXX : XXX (XXX.X%)	0.XXXX
~ High-flow oxygen	XXX : XXX (XXX.X%)	0.XXXX
~ Supplemental oxygen	XXX : XXX (XXX.X%)	0.XXXX
~ Noninvasive ventilation	XXX : XXX (XXX.X%)	0.XXXX
~ Extracorporeal membrane oxygenation (ECMO)	XXX : XXX (XXX.X%)	0.XXXX
~ Other	XXX : XXX (XXX.X%)	0.XXXX
Prone position	XXX : XXX (XXX.X%)	0.XXXX
. Days with Mechanical Ventilation [days]		TW
N (Missing)	XXX (XXX)	0.XXXX
Mean (SD)	XXX (XXX)	
Median (IQR)	XXX (XXX)	
Q1~Q3	XXX~XXX	
Min~Max	XXX~XXX	

Prior Procedure: procedures onset prior to Day 1

Concomitant Procedures: procedures from Day 1 to End of Treatment Visit

Post Procedure: procedures after End of Treatment Visit to End of Study

Day# = End date/time – Start date/time, rounded up to the nearest integer

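### SAP 14.1.8 splits the tested supportive-care comparisons at the End of Treatment Visit, which stopping study drug can bring forward in Arm A only

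*SAP*

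**What the plan says.** Table 14.1.8 of the SAP uses the ITT population. It tests each type of supportive-care procedure between arms (chi-square or Fisher) and days of mechanical ventilation (t test or Wilcoxon). The layout is repeated for three periods: "Repeat Duration: Prior Procedure, Concomitant Procedure, Post Procedure". The footnotes set the boundary between the last two: "Concomitant Procedures: procedures from Day 1 to End of Treatment Visit" and "Post Procedure: procedures after End of Treatment Visit to End of Study". There is no row for the whole study.

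SAP 1.1 gives Visit 6 more than one meaning: "Visit 6 is End of Treatment (EOT) Visit, Treatment Discontinuation Visit or Early Withdrawal Visit at/before EOT". It then adds a correction: "Data of visit 6 not in its visit window will be shifted to corresponding scheduled visit for analysis". That correction is marked for symptoms, the NIAID scale, laboratory tests, and vital signs with SpO2 and clinical signs. Procedures are not listed. The visit list in the SAP's instructions places Visit 6 at Day 14 ± 1. Section 14.1.8 does not say which date applies to a patient whose Visit 6 came early.

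In the protocol, only Arm A receives CX-4945 (sections 6.1.2 and 9.1). Section 4.3 keeps patients under observation after they stop it: "Patients who discontinued therapy should remain in the study and continue follow-up for key outcomes".

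**The concern.** The end of the Concomitant period can be set by something that happens after randomization, and stopping study drug can happen in one arm only. Suppose a patient in each arm starts supplemental oxygen on Day 7. If the Arm A patient had a discontinuation visit on Day 4, that oxygen is a Post procedure. In Arm B it is a Concomitant one. The clinical courses are the same but the labels differ.

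The Concomitant difference then moves in favour of CX-4945 and the Post difference moves against it. The cut-off may also carry information about outcome, because protocol sections 6.1.5 and 7.3 list disease progression among the reasons for stopping treatment. Two tested comparisons would then partly reflect who stopped drug, and the table has no row that compares the arms over a common period.

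**Working it through.** The documents give no figure to reproduce here. The sample size rests on clinical judgment, with no power calculation (protocol 9.3). The first step is a reading of the rules; the arithmetic after it only gives a sense of scale.

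**Which procedures move.** Let s be the day of an early discontinuation visit in Arm A.
- Start on or before Day s: Concomitant, as in Arm B.
- Start after Day s and by Day 14: Post in Arm A, Concomitant in Arm B.
- Start after Day 14: Post in both arms.

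Only the middle group is affected.

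**Length of the periods.** From the documents: about 20 patients randomized 1:1, so about 10 per arm; End of Treatment nominally Day 14; last follow-up Day 60. Assumed: k = 1 to 3 Arm A patients have a discontinuation visit on Day s = 4, 8 or 11, and everyone else has Visit 6 on Day 14.

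Arm B Concomitant = 10 × 14 = 140 patient-days. Arm A Concomitant = (10 − k) × 14 + k × s:

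| k | s = 4 | s = 8 | s = 11 |
|---|---|---|---|
| 1 | 130 (−7.1%) | 134 (−4.3%) | 137 (−2.1%) |
| 2 | 120 (−14.3%) | 128 (−8.6%) | 134 (−4.3%) |
| 3 | 110 (−21.4%) | 122 (−12.9%) | 131 (−6.4%) |

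Arm B Post = 10 × 46 = 460. Arm A Post = (10 − k) × 46 + k × (60 − s), from 463 (k = 1, s = 11; +0.7%) to 490 (k = 3, s = 4; +6.5%).

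**Expected counts with no treatment effect.** Assume a constant hazard, equal in both arms, giving a 20% risk of a procedure by Day 14. With k = 3 and s = 4, an early stopper's risk within the shortened period is 1 − 0.8^(4/14) = 0.062. Arm A's expected number of patients with a Concomitant procedure is 7 × 0.20 + 3 × 0.062 = 1.59, against 10 × 0.20 = 2.0 in Arm B.

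**Limiting case for the p-value.** Suppose m of 10 patients in each arm have a procedure by Day 14, and all m in Arm A start after an early discontinuation visit. A fixed Day 1 to 14 period gives m/10 v m/10, p = 1.0. The visit-tied period gives 0/10 v m/10. The expected count in each event cell is then m/2, below 5 in two of the four cells for every m used here, so the rule in SAP 3.2 selects Fisher's exact test:

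| m | 2 | 3 | 4 | 5 |
|---|---|---|---|---|
| Fisher p | 0.47 | 0.21 | 0.087 | 0.033 |

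The p-value falls below 0.05 only at m = 5, which needs half of Arm A to stop early and then start a procedure by Day 14. Each relabelled patient changes Arm A's Concomitant incidence by 1/10, or 10 percentage points.

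**The case against.** The strongest reply is that this is a gap in a supportive table and not a demonstrated bias. Table 14.1.8 sits in the section on demographic and baseline data. Death, respiratory failure and hospitalization are tabulated in 14.2.4.1 from the NIAID scale or adverse events, with no cut at the End of Treatment Visit. The patients are outpatients, with severe and critical illness excluded at entry, so procedures may be few. The visit list gives Day 14 ± 1, and 14.1.8 never states that an early Visit 6 closes the period. Arm B's Visit 6 can also come early through study withdrawal.

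Most of that stands, and it limits the consequence. It does not remove the fault. SAP 1.1 is the SAP's only statement of what Visit 6 is when treatment stops early, and its correction leaves procedures out. Early withdrawal is not a matching event: leaving the study generally limits what is observed later, whereas stopping drug leaves the patient under observation and moves recorded events across the boundary. Table 14.2.4.1 does not replace 14.1.8 fully either. Home oxygen is pooled with activity limitation in NIAID item 7, and fluid management, prone positioning and ventilation days are tested only in 14.1.8.

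A reader might infer four stronger things that the documents do not support:
- *The procedures are lost.* They appear in the Post block of the same table.
- *The period ends on the last dose date.* SAP 1.1 names a visit, not a dose date.
- *Ventilation that leads to stopping drug is moved out.* Protocol 6.1.5 lists "Respiratory failure requiring invasive mechanical ventilation" among the reasons to discontinue, but ventilation that prompts the stop starts on or before the discontinuation visit and stays Concomitant.
- *Days on a procedure are cut short.* The footnote counts days from the start to the end of the procedure, with no truncation at the visit. How a spanning procedure is allotted is not stated, but that is a separate gap.

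**Conclusion.** The point holds as a defect in the period definition. Read with SAP 1.1, the boundary in 14.1.8 can depend on treatment arm, and the Concomitant and Post differences then shift in opposite directions with no combined row to fall back on.

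Its size depends on how many Arm A patients stop early and when, which the documents do not give. Under the stated assumptions Arm A's Concomitant period is 2% to 21% shorter than Arm B's; the 21% is the far end, with three of ten stopping on Day 4. The distortion is larger if the progression that leads to stopping also leads to a later procedure, and it is zero if every procedure starts on or before the discontinuation visit.

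It would be wrong to conclude that the trial's efficacy or safety results are biased by this: no primary or secondary endpoint uses these periods. The change is still worth making, because it takes a treatment-dependent cut-off out of tested comparisons.

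**What to change.** In the footnotes to SAP 14.1.8, define the periods by study day in both arms: Concomitant from Day 1 to Day 14, and Post from Day 15 to end of study. Add one row covering Day 1 to end of study and make it the between-arm comparison. State how a procedure that spans the boundary is counted, for patients and for days. If an on-drug period for Arm A is of interest, show it descriptively without a p-value.

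The cost is a few footnote lines and one table row. The procedure start and end dates/times that the table already uses are enough, so no new data are needed.

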### 14.1.9 Study Drug Administration, Compliance and Exposure

Population: Intent-to-Treat Population

Characteristics	CX-4945
. Repeat Variable:	
Treatment Duration [days],	
Total CX-4945 Dose [caps],	
Mean Daily Dose [caps / day]	
Total CX-4945 Administration [Times],	
Treatment Compliance [%], Mean Daily Administration [times / day]	
N (Missing)	XXX
Mean (SD)	XXX (XXX)
Median (IQR)	XXX (XXX)
Q1~Q3	XXX~XXX
Min~Max	XXX~XXX
. Treatment Compliance	
N (Missing)	XXX (XXX)
<50%	XXX (XXX.X%)
50 ~ <75%	XXX (XXX.X%)
75 ~ <100%	XXX (XXX.X%)
100 ~ <125%	XXX (XXX.X%)
≥125%	XXX (XXX.X%)
. CX-4945 Completion	
N	XXX
CX-4945 Completed	XXX (XXX.X%)
CX-4945 Not Completed	XXX (XXX.X%)
~ Drug Interruption	XXX (XXX.X%)
~ Drug Discontinuation	XXX (XXX.X%)
~ <Reason 1>	XXX (XXX.X%)
~ <Reason 2>	XXX (XXX.X%)
...	...

Treatment Duration [days] = the last administration date – the first administration + Adjustment

The first administration time	The last administration time	Adjustment
Morning	Morning	+0.5
Morning	Evening	+1
Evening	Morning	+0
Evening	Evening	+0.5

Mean Daily Dose [caps / day] = Total CX-4945 Dose [caps] / Treatment Duration [days]

 Treatment Compliance [%] =  $\frac{\text{# of times of CX-4945 actually administered}}{(\text{Treatment Duration}) * (2 \text{ times of administration/day})} * 100\%$ 

Mean Daily Administration [times / day] = Total CX-4945 Administration [Times] / Treatment Duration [days]

## 14.2 EFFICACY DATA

### <TTR Layout: For Time to Response Data>

Population: Intent-to-Treat Population / Per-Protocol Population

Characteristics	Treatment Group	Difference	P-value
--Repeat Population: <See populations above>			

- Variable per table title:

Time to COVID-19-Related Clinical Signs Normalization [days]

Time to COVID-19-Related Symptoms Resolution [days]

[figure not shown]
Time to SARS-COV-2 Viral Clearance [days]

. Repeat Scenario: Best Case Scenario, Worst Case Scenario

N (Missing)	XXX (XXX)	LOGRANK
Censored No.	XXX (XXX%)	0.XXXX
Observed No.	XXX (XXX%)	
Q1 [95% CI]	XXX [XX~XX]	
Median [95% CI]	XXX [XX~XX]	
Q3 [95% CI]	XXX [XX~XX]	
Mean (SE)	XXX (XXX)	
Min	XXX	
Max (Observed)	XXX	
Max	XXX	

*Footnote the definition according to [Instructions and Abbreviations] of title pages.*

### <TTR Figure Layout: For Response Proportion>

## 14.2.1 COVID-19-Related Clinical Signs

### 14.2.1.1 Time to COVID-19-Related Clinical Signs Normalization

*Use TTR Layout*

*Footnote: refer to table 14.3.8 for the normal status of each symptom by visit*

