9.7. GENERAL STATISTICAL CONSIDERATIONS

All collected study data will be presented in patient data listings. Statistical analyses will be performed using SAS® for Windows, version 9.4 or later. Descriptive statistics (n, mean, standard deviation, median, minimum and maximum) will be presented by treatment group for continuous variables. Frequencies and percentages will be presented by treatment group for categorical variables.

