### 1.4.2 Method for Time to Event Data

The endpoints about time to event data as below table will be compared between treatment groups by using log-rank test, and corresponding response proportion will be presented by using Kaplan-Meier methods.

- Time to COVID-19-Related Clinical Signs Normalization
- Time to Oxygen Saturation Level Normalization
- Time to moderate COVID-19-Related Symptoms Resolution
- Time to SARS-COV-2 Viral Clearance
- Time to Improvement on NIAID 8-Point Clinical Progression Outcomes Scale (additional analysis, not mentioned in the protocol)
- Time to Improvement on EQ-5D-5L Imaginable Health Status (additional analysis, not mentioned in the protocol)

Considering the early censor on time to response (Normalization / Recovery / Viral Clearance / Improvement) data will result in over optimistic in statistical results, two data estimation methods below will be used for the sensitive analyses. Results will be claimed as robust if the results of both methods are consistent.

Time to Response (days), Best Case Scenario  
= Days to first response for responder,  
= Days to last observation for non-responder (censored)

Time to Response (days), Worst Case Scenario  
= Days to first response for responder,  
= Days to planned last observation date (31 for EQ-5D-5L and SARS-COV-2 Viral Clearance at visit 7, 45 for others at visit 8) for non-responder (censored)

Days to first response = date of first response – the first treatment date/time + 1  
Days to last observation = date of last evaluation – the first treatment date/time + 1  
For Arm SOC, the first treatment date is the date of visit 2

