## (5) Efficacy Endpoints:

- **Time to COVID-19-Related Clinical Signs Normalization: Normal when all below are met**
  - (1) Fever is <36.6°C from axillary site, or < 37.2°C from oral site, or < 37.8°C from rectal or tympanic site, or <37.2°C from forehead by using non-contact infrared thermometers
  - (2) Respiratory rate is < 20 bpm while breathing room air
  - (3) SpO2 ≥ 96% in room air without shortness of breath or dyspnea caused by COVID-19
  - (4) Heart rate < 90 beats per minute

If some signs listed above were caused by other conditions documented in the medical history and started before COVID-19, the patient can be considered as recovered, when these signs return to the previous (pre-COVID-19) values
- **Oxygen Saturation Level Normalization: Normal when SpO2 ≥ 96%**
- **Resolution of moderate COVID-19-Related Symptoms when all below are met:**
  - No key COVID-19-related symptoms scored higher than 1.
  - If some symptoms were caused by other conditions documented in the medical history and started before COVID-19 (e.g, insomnia), the patient can be considered as recovered, when these symptoms return to the previous (pre-COVID-19) value.
- **SARS-CoV-2 Viral Clearance: negative RT-PCR**

- **NIAID 8-Point Clinical Progression Outcomes Scale:**
  - 1 - Death
  - 2 - Hospitalized, on invasive mechanical ventilation or extracorporeal membrane oxygenation (ECMO)
  - 3 - Hospitalized, on non-invasive ventilation or high flow oxygen devices
  - 4 - Hospitalized, requiring supplemental oxygen
  - 5 - Hospitalized, not requiring supplemental oxygen - requiring ongoing medical care (COVID-19 related or otherwise)
  - 6 - Hospitalized, not requiring supplemental oxygen - no longer requires ongoing medical care
  - 7 - Not hospitalized, limitation on activities and/or requiring home oxygen
  - 8 - Not hospitalized, no limitations on activities
- **EQ-5D-5L Imaginable Health Status Improvement: Imaginable Health Status <90 at baseline and ≥ 90 after baseline**
- **Time to Response (Normalization / Resolution / Viral Clearance / Improvement)**

Time to Response (days), Best Case Scenario  
 = Days to first response for responder,  
 = Days to last observation for non-responder (censored)

Time to Response (days), Worst Case Scenario  
 = Days to first response for responder,  
 = Days to planned last observation date (31 for EQ-5D-5L and SARS-COV-2 Viral Clearance at visit 7, 45 for others at visit 8) for non-responder (censored)

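### The SAP's time-to-response tables print a mean for censored data with no restriction time, so the two arms' means may not be comparable

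*SAP*

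**What the plan says.** The operative text is the TTR Layout at the start of SAP 14.2. For each arm, for the ITT and PP populations and under both scenarios, it lists N, censored and observed counts, quartiles with 95% CIs, Mean (SE), Min, Max (Observed) and Max, with a log-rank p-value. Table "14.2.1.1 Time to COVID-19-Related Clinical Signs Normalization" brings it in with the instruction "Use TTR Layout", as do 14.2.1.4, 14.2.2.1, 14.2.3.2, 14.2.4.2 and 14.2.5.2.

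On method, SAP 1.4.2 says that the endpoints "will be compared between treatment groups by using log-rank test" and that the "corresponding response proportion will be presented by using Kaplan-Meier methods". A non-responder's time is:

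- Best Case: "Days to last observation for non-responder (censored").
- Worst Case: "Days to planned last observation date (31 for EQ-5D-5L and SARS-COV-2 Viral Clearance at visit 7, 45 for others at visit 8"). This is also a censored time, as SAP Instructions item (5) repeats: "45 for others at visit 8) for non-responder (censored").

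Protocol 9.7 states "Statistical analyses will be performed using SAS® for Windows, version 9.4 or later", without naming a procedure or option. SAP Instructions item (8) explains the mean only as the mean of the values and has no entry for the SE. Neither document gives a time to which the mean is restricted.

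**The concern.** The mean of a Kaplan-Meier distribution is the area under the curve of the proportion not yet recovered. If the longest time in an arm is censored, the curve never reaches zero and the mean is undefined unless an upper limit is set. Under the SAP's rules this happens in any arm where a non-responder's censored time exceeds the last response, which is the usual situation when someone completes follow-up unrecovered.

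With no limit in the plan, the software or the programmer chooses one. If the choice is each arm's own last response, non-responders add nothing after that day, and an arm whose responses stop early gets a short mean because many of its patients never respond. With about 10 patients per arm and no power calculation (Protocol 9.3), readers will lean on descriptive figures, and a mean number of days to recovery or viral clearance is easily quoted on its own.

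**Working it through.** The plan gives no numerical mean to reproduce, so the data below are hypothetical. They use about 10 per arm (Protocol 9.3), the planned visit days and the SAP's censoring rules.

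**Main example, Worst Case, limit Day 45**

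- SOC: 5 respond on Day 8; 5 never respond and are censored on Day 45.
- CX-4945: 5 respond on Day 8, 4 on Day 14, 1 on Day 28.

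Kaplan-Meier mean to limit τ = area under S(t) from 0 to τ.

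| Reading of the mean | SOC | CX-4945 |
|---|---|---|
| Cut at own last response | 1 × 8 = 8.0 | (5×8 + 4×14 + 28)/10 = 12.4 |
| Common Day 45 | 8 + 0.5 × (45 − 8) = 26.5 | 12.4 |
| Plain average of listed times | (5×8 + 5×45)/10 = 26.5 | 12.4 |

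Under the first reading SOC looks 12.4 − 8.0 = 4.4 days faster. Under the other two it is 26.5 − 12.4 = 14.1 days slower.

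Log-rank test on the same data, SOC arm: observed responses 5; expected 10×10/20 + 4×5/10 + 1×5/6 = 5 + 2 + 0.83 = 7.83; observed minus expected = −2.83; p about 0.05. The test favours CX-4945, so under the first reading the mean and the p-value in one table would point in opposite directions.

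**Viral clearance, limit Day 31**

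- Arm X: 3 clear on Day 8, 2 on Day 14, 5 never.
- Arm Y: 3 on Day 8, 3 on Day 14, 4 on Day 28.
- Own last response: X = 8 + 0.7×6 = 12.2; Y = (3×8 + 3×14 + 4×28)/10 = 17.8.
- Common Day 31: X = 12.2 + 0.5×17 = 20.7; Y = 17.8. The order changes.

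**When it does not reverse.** In the main example, move one SOC response from Day 8 to Day 28. The own-last-response mean becomes 8 + 0.6×(28 − 8) = 20.0, against 12.4, which is the right order.

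**Plain average in the Best Case.** Return to the main example.

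- If one SOC non-responder leaves on Day 4, the plain average is (5×8 + 4×45 + 4)/10 = 22.4. Early departure without recovery has shortened the mean by (45 − 4)/10 = 4.1 days.
- If all five non-responders are last seen on Day 11, it is (5×8 + 5×11)/10 = 9.5, below the 12.4 of the arm in which everyone recovered.

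**How often, under the own-last-response reading.** Assumptions: exponential recovery with mean 10 days, detected at Days 4, 8, 11, 14, 28 and 45; 10 per arm; 4,000 simulated trials per setting.

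| Ever respond | Worse arm has the shorter mean, own last response | Same, common Day 45 |
|---|---|---|
| 95% v 60% | 29% | 7% |
| 90% v 50% | 34% | 5% |

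Repeat runs gave 30% v 6% and 31% v 4%. At 95% v 60% the average means are 14.3 v 19.0 (own last response) and 15.1 v 26.1 (Day 45). On average the order is right, but the gap shrinks from 11.0 to 4.7 days. A different set of assumptions (all recover v 50%, with early to late response patterns) gave reversal in 21% to 32% of trials, against 0.3% to 4% with a common limit.

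**The case against.** A reader might infer that the SAP plans a mean cut at each arm's last response. It does not say so. It applies Kaplan-Meier methods to the response proportion, the protocol names only SAS, and the abbreviation list explains the mean as an ordinary mean of values. On that literal reading the Worst Case example gives 26.5 v 12.4 and nothing reverses. This objection stands, and it makes the reversal conditional.

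It does not clear the row. The layout gives an SE where the SAP's ordinary summaries give an SD, and it sits among quartiles with CIs and censored counts, so a survival-procedure mean is at least as plausible. The literal reading also fails in the Best Case, as shown above, and SAP 1.4.2 itself warns that early censoring makes results over-optimistic.

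It is also fair that little depends on this row. The comparison is the log-rank test. In the main example the same table would show SOC with 50% censored, Max (Observed) 8 and Max 45, and response-proportion figures follow. The response rates in the simulations are assumptions with no basis in the documents. All of this limits the severity, and it stands.

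**Conclusion.** The point holds in conditional form. The TTR Layout prints a mean for censored data without saying what it estimates or where it stops, and under either plausible reading it misleads in at least one scenario. If each arm is cut at its own last response, the means are not comparable and can reverse (8.0 v 12.4 against 26.5 v 12.4 in the example). If it is a plain average, the Worst Case is sound but the Best Case treats a drop-out day as a recovery day.

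Two stronger conclusions are not supported. Reversal is not to be expected in every trial: it depends on when the poorer arm's last response falls, and under the assumed scenarios it occurs in roughly a fifth to a third of trials. Nor is the trial's comparison compromised, because the mean is descriptive and the log-rank test does not use it. I make no claim about the size of the SE. Severity is minor to moderate.

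**What to change.** In the TTR Layout of SAP 14.2, do one of the following:

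- Delete the Mean (SE) row. The quartiles, censored counts, log-rank test and figures remain.
- Define the row as the Kaplan-Meier restricted mean time to response, up to one pre-specified limit common to both arms, and footnote that limit. Use the SAP's own days: 31 for RT-PCR clearance and EQ-5D-5L, 45 for the other endpoints. If follow-up in either arm does not reach that day, use the largest time that both arms support, and write this rule down in advance.

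A between-arm difference with 95% CI in the existing Difference column is optional. Across six tables, two scenarios and two populations it would add 6 × 2 × 2 = 24 intervals at about 10 per arm.

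The cost is one table row, a footnote and a programming setting. The downside is small: the limit has to be stated, and a response after it is not counted in the mean. For example, a response on Days 46 to 48, which the Visit 8 window (45 ± 3) allows, would enter as 45 days.
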